10. ETHICAL CONSIDERATIONS

10.1 Regulation statement

The study will be conducted according to the principles of the Declaration of Helsinki (version, date, see for the most recent version: www.wma.net) and in accordance with the Medical Research Involving Human Subjects Act (WMO) and other guidelines, regulations and Acts

10.2 Recruitment and consent

For this study a cluster randomized design - instead of a randomisation at patient level - was chosen to minimize logistic problems, optimize inclusion of patients and limit bias during the study. The cross-over design was chosen to prevent influences by center, as the inter-center variability in facility and treatment can influence outcome of treatment. Differences which are found can now be attributed solely to the intervention as the center serves as its own control. As this study will be performed in several centres with random start with standard care or with TDM-tailored treatment, we anticipate that the time-based biases will be negligible. This design was previously successfully used in the Netherlands [32]. Following the design of this study a patient does not have to specially recruited for start of the treatment. So no informed consent has to be asked for starting the treatment. The physician asks the patients at day two of fever via regular procedures, commonly used for EORTC/HOVON studies whether clinical data can be used for study purposes and additional in the control group whether control samples can be drawn. If the patient agrees the data is used, if not data are not used. For this decision a regular time of 1 day is given to the patient to think of participation.

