4.4 Sample size calculation

In a previous randomized trial with voriconazole in a dosage according to product leaflet with similar inclusion criteria the response was: complete in 20%, partial in 30%, stable in 10% and failure in 40% [16]. As TDM will probably result in the largest benefit in patient with low voriconazole trough levels, who are not responding, or in patients with high trough levels, who stopped because of side effects, the sample size calculation of this study is based on the reduction of patients failing on voriconazole therapy. For control patients (treated without TDM) a failure rate of 40% is expected [16], while for patients during the experimental TDM episode, a failure of 20% is expected. Under the most unfavourable assumption that the intra cluster correlation coefficient equals the intra period correlation coefficient varying between 0.002 and 0.02, and knowing that at least 12 centres are participating in this study, each cluster must include 16 patients to obtain a power of about 80% with an unreliability of 5% (two-sided) to detect a clinically relevant improvement of 20% of reduction of patients failing on voriconazole at day 28 of treatment compared to control. This means that in total 192 patients are necessary for performing this study. To compensate for loss during follow-up in total 200 patients will be included. Loss during follow-up is defined as patients not willing to continue participation because of personal reasons. Patient stopping because of voriconazole adverse effects are noted as "failure".

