7.1.3 Other study parameters (if applicable)

A set of patient characteristics and clinical parameters is used for baseline characteristics of the control and intervention group:

- age, gender, weight, BMI
- parameters for EORTC/MSG classification
- underlying medical condition and previous/ongoing treatment for haematological malignancies
- co-medication: agents which influences pharmacokinetics of voriconazole, immunosuppressive agents (corticosteroids, ciclosporin, MMF)
- Pharmacogenetics (CYP450 2C9 and 2C19)
- For the economical evaluation (cost effectiveness if TDM) of this study the costs of both treatment arms are evaluated. The costs of hospital and ICU stay, diagnostic procedures, used medication and blood product are evaluated, Also quality of life and production loss is evaluated after release from the hospital.
- for detailed information see CRF.

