7.3 Study procedures

- 1) At day two of fever the patients is informed about the study and a 24 hour period is given to think of participation.
- 2) The haematologist, in consultation with a medical microbiologist or infectious diseases specialist, will decide to start voriconazole therapy in a patient with suspected IA based on EORTC/MSG criteria. A HRCT scan is crucial part of the procedure for diagnosing the invasive fungal disease. Triggers for ordering an HRCT include detection of galactomannan in serum or plasma, pulmonary complaints or abnormalities seen on X-ray and unexplained fever of > 4 days despite broad-spectrum antibiotic therapy. A HRCT is performed at start of voriconazole treatment +/- 3 days.
- 3) Voriconazole serum concentrations after the 5th dosage (IV 6mg/kg for the first 24 hours followed by 4mg/kg bid, PO 400mg for the first 24 hours followed by 200mg bid) will be measured in all patients during treatment with voriconazole during the TDM period. Two blood samples will be drawn, one immediately before the dose (t= 0) and one 2h after the dosage (t=2) when administered orally or 1h after the end of infusion

when administered intravenously. If the serum trough level is < 2.0 mg/L the dosage will be increased. If the serum trough level is > 5mg/L the dosage will be reduced. Dosage adjustment will be performed according to a standard algorithm. Also a sample (5ml) will be drawn to assess CYP450 2C9 and 2C19 polymorphisms.

- 4) Three days after dosage adjustment a control sample series is drawn, followed by the same dose adjustment algorithm.
- 5) After reaching the therapeutic window trough levels, surveillance samples will be drawn twice a week while the patient is in the hospital. For outpatient treatment trough levels will be drawn at regular visits of the patients to the outpatient clinic (about once every two weeks). Since outpatients are clinically more stable, fluctuations are expected to be less frequent, moreover patients are often put on voriconazole during hospital stay and have a stable level when leaving the hospital. In the period without TDM, serum samples will be stored and used later to evaluate serum trough levels during the standard care episode. During this period, no additional vena punctures will have to be performed for the purpose of the study as the blood samples will be taken during regular sampling on the morning round. In total 16-54ml will be drawn depending on the duration of treatment.

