7.4 Withdrawal of individual subjects

Subjects can leave the study at any time for any reason if they wish to do so without any consequences. Withdrawal from the study means that the patient does not allow the investigator to use the medical data for study purposes (intervention group) or does not allow the investigator to use the medical data for study purposes and taking control samples (control period).

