9. STATISTICAL ANALYSIS

The endpoints with respect to percentages at day 7, day 28 (including the primary endpoint) and at 12 weeks will be analyzed using hierarchical models where intervention effects, (random) cluster effects, and random cluster-period effects will be analyzed. Time to events (for example response or death) will be analyzed using Kaplan Maier curves with log rank tests and Cox regression models.

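### Consent is sought once the period's arm is set and asks more of control patients, so entry into the analysis can depend on arm and the claim that differences are due to the intervention alone is too strong.

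*Protocol*

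**What the plan says.** **Allocation.** The order of two 12-month periods is randomised per centre (Summary; section 3), so a patient's arm is settled before anyone approaches that patient. Section 3 explains why the intervention is not blinded. Only the expert panel is unaware of allocation (sections 3 and 8.4).

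**Entry.** Treatment with voriconazole is an inclusion criterion (section 4.2). The haematologist, after consultation, "will decide to start voriconazole therapy in a patient with suspected IA based on EORTC/MSG criteria" (section 7.3).

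**Consent.** At day two of fever the physician asks "whether clinical data can be used for study purposes and additional in the control group whether control samples can be drawn" (section 10.2). Without agreement the data are not used. Withdrawal is defined by arm in the same way: in the intervention group it covers data use only, while a control patient "does not allow the investigator to use the medical data for study purposes and taking control samples (control period" (section 7.4).

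**Analysis.** Section 9 lists "hierarchical models where intervention effects, (random) cluster effects, and random cluster-period effects will be analyzed" and names no patient-level covariate. Section 7.1.3 collects "parameters for EORTC/MSG classification", with the stated use of describing the two groups.

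**Claim.** Sections 3 and 10.2 say that differences found can be put down to the intervention alone, because each centre is its own control.

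**The concern.** Randomising the order of periods balances centres, not the patients who enter within a period. If the wording of a request, or the readiness to make it, differs by arm, the two sets of analysed patients can differ in prognosis even when TDM has no effect.

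There is room for this. Section 4.1 works with refusal and competing studies together removing half of the potentially eligible patients. It also calls the population heterogeneous and puts possible disease at 100 of about 200 national cases a year. A shift in the mix of possible versus probable/proven disease would feed straight into the failure rate.

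The analysis in section 9 would not remove it. A random cluster effect absorbs stable differences between centres. A random cluster-period effect absorbs variation that is unrelated to arm. A shift that runs the same way with arm in every centre is carried by the intervention effect.

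**Working it through.** **1. The plan's own figure.** Section 4.4 gives "a failure rate of 40% is expected" for controls, 20% under TDM, a two-sided 5% level, and "at least 12 centres are participating in this study, each cluster must include 16 patients to obtain a power of about 80" per cent, so 12 × 16 = 192.

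- Per arm without clustering: n = [1.96·√(2·0.3·0.7) + 0.842·√(0.24 + 0.16)]² / 0.20² = 81.2, so 82.
- Design effect with 8 patients per cluster-period, correlation 0.02 and no credit for between-period correlation: 1 + 7 × 0.02 = 1.14.
- 82 × 1.14 = 93.5, so 94 per arm and 188 in all, close to 192. Power at 96/1.14 per arm is 81.4%.

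The sample size reproduces and is not in dispute. It supplies the 96 per arm used below.

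**2. Consent by arm.**

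| | TDM period | Control period |
|---|---|---|
| Asked for (10.2) | data use | data use and control samples |
| Withdrawal covers (7.4) | data use | data use and control samples |
| Refuses data use | data not used | data not used |
| Allows data use, declines samples | cannot arise | not stated |

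That physicians know the arm is an inference, but a firm one: doses are adjusted by level only in TDM periods (section 6.6), and the question put to the patient is itself different.

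**3. Size of a possible bias.** The documents give no failure rate by EORTC/MSG class and no refusal rate by arm, so these inputs are assumptions:

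- failure in possible versus probable/proven disease of 30%/50% (gap 0.20) or 25%/55% (gap 0.30), each giving 40% overall at a 50:50 mix;
- share of possible disease shifted by 5, 10 or 15 points in one arm;
- no true TDM effect, 96 per arm, no clustering.

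Bias = shift × gap. SE = √(2·0.4·0.6/96) = 0.0707. Type I error = P(|Z + bias/SE| > 1.96).

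| Shift | Gap 0.20: bias, type I | Gap 0.30: bias, type I |
|---|---|---|
| 5 points | 1.0 points, 5.2% | 1.5 points, 5.5% |
| 10 points | 2.0 points, 5.9% | 3.0 points, 7.1% |
| 15 points | 3.0 points, 7.1% | 4.5 points, 9.7% |

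Example: 0.15 × 0.30 = 0.045; 0.045/0.0707 = 0.64; error 9.7%. With the design effect of 1.14 the SE is 0.0755 and this cell becomes 9.2%.

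**4. The other direction.** If the shift runs against TDM, the cost is power. With p₂ = 0.20 + bias and p̄ the mean of 0.40 and p₂, power = Φ[(0.40 − p₂ − 1.96·√(2p̄(1 − p̄)/96)) / √((0.24 + p₂(1 − p₂))/96)]. This is 86.2% with no bias, 82.1% at 1 point and 63.4% at 4.5 points, before clustering.

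**The case against.** Several features of the protocol limit the problem, and they stand.

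- **Timing.** Consent is sought at day two of fever, with 24 hours to decide. The voriconazole decision is a later step, and one trigger for the diagnostic CT is unexplained fever of more than 4 days. Consent will often precede the scan and the EORTC/MSG class, so it has limited scope to select on that class. Other triggers, such as galactomannan, can come sooner.
- **Burden.** Control samples come from the routine morning round, with no extra venepuncture (section 7.3). The second request is light, though it is still a second request.
- **Same drug in both periods.** Only dosing differs, and the start rests on EORTC/MSG criteria after consultation. No reason is given why readiness to start should differ by arm.
- **Blinded panel.** It classifies disease and reviews the primary endpoint. That protects assessment, not who enters.

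Three stronger readings are tempting, and the documents do not support them.

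- A reader might infer that a control who declines samples loses the outcome data. Section 10.2 more naturally ties loss of data to the data-use answer, and section 7.4 joins the two items. The text is ambiguous, not adverse.
- A reader might infer that the primary analysis is unadjusted. Section 9 is a brief outline that names no covariate, and a statistical analysis plan that is not shown could add some.
- A reader might take 10% as the expected error rate, with TDM favoured. It is the top of an assumed range, and nothing indicates the direction. The 100 of 200 figure is national yearly incidence, not the trial's planned mix.

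**Conclusion.** The point holds in a limited form. The arm is fixed, and very probably known, before consent. The request differs by arm, refusal removes data, and the handling of a control who declines only samples is left open. Entry into the analysed set can therefore depend on arm, and neither the crossover nor the random effects in section 9 correct that. The statement in sections 3 and 10.2 that differences are due to the intervention alone claims more than the design delivers: the crossover removes stable centre differences only.

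Early consent, routine sampling and the blinded panel reduce the possible bias without removing it. On the assumed rates and shifts it is about 1 to 4.5 points in either direction, against a planned effect of 20 points, with a two-sided type I error of about 5% to 10%. These figures show what is possible. They do not estimate what will happen. The case for acting is that the mechanism is written into the consent procedure and is cheap to take out.

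**What to change.** 1. **Consent (sections 10.2 and 7.4).** Ask the same data-use question in both periods. Make control samples a separate optional item, and state that declining it, or withdrawing from it later, does not remove the patient's outcome data.
2. **Primary model (section 9).** Add baseline EORTC/MSG class, possible versus probable/proven, as a fixed covariate, as classified from baseline data by the panel unaware of allocation. The data are already collected, and section 4.1 already applies the definitions at baseline. This corrects only for measured class, so it supplements the consent change and does not replace it.
3. **Attribution sentence (sections 3 and 10.2).** Limit it to stable differences between centres, and acknowledge that patient selection may differ between periods.

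The cost is a revised consent sheet, one more model term, and some controls without stored levels for secondary endpoint 3. No dose or clinical rule changes.

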10.3 Objection by minors or incapacitated subjects (if applicable)

Not applicable

10.4 Benefits and risks assessment, group relatedness

Retrospective observational studies of voriconazole serum concentration suggest that serum concentration correlate with toxicity and clinical response. The objective of this study proposal is to determine whether pharmacologic optimization of voriconazole by means of therapeutic drug monitoring (TDM) results in improved patient outcomes (efficacy and safety) and is more cost-effective compared to the current standard of care. The patients in the intervention population possibly benefit from the intervention, as toxicity and sub therapeutic concentration could be prevented. In the control group

patients receive standard of care. The latter group will also probably benefit from this trial as patients in trials tend to get more attention from medical staff.

10.5 Compensation for injury

As there is no additional risk for participation in this study the Medical Ethics committee of the UMCG granted exemption from liability insurance (art. 4 lid 1 Besluit verplichte verzekering bij medisch-wetenschappelijk onderzoek met mensen).

10.6 Incentives (if applicable)

Not applicable

11. ADMINISTRATIVE ASPECTS AND PUBLICATION

11.1 Handling and storage of data and documents

Data is handled confidentially. A subject identification code list is used to link the data to the subject. The code is based on a clusternumber, abbreviation of the center and number of inclusion (e.g. 1-UMCG-12). The key to the code should be safeguarded by the investigator. The handling of personal data complies with the Dutch Personal Data Protection Act.

11.2 Amendments

A 'substantial amendment' is defined as an amendment to the terms of the METC application, or to the protocol or any other supporting documentation, that is likely to affect to a significant degree:

- the safety or physical or mental integrity of the subjects of the trial;
- the scientific value of the trial;
- the conduct or management of the trial; or
- the quality or safety of any intervention used in the trial.

All substantial amendments will be notified to the METC and to the competent authority.

Non-substantial amendments will not be notified to the accredited METC and the competent authority, but will be recorded and filed by the sponsor.

11.3 Annual progress report

The sponsor/investigator will submit a summary of the progress of the trial to the accredited METC once a year. Information will be provided on the date of inclusion of the first subject, numbers of subjects included and numbers of subjects that have completed the trial, serious adverse events/ serious adverse reactions, other problems, and amendments.

11.4 End of study report

The sponsor will notify the accredited METC and the competent authority of the end of the study within a period of 90 days. The end of the study is defined as the last patient's last visit.

In case the study is ended prematurely, the sponsor will notify the accredited METC and

the competent authority within 15 days, including the reasons for the premature termination.

Within one year after the end of the study, the investigator/sponsor will submit a final study report with the results of the study, including any publications/abstracts of the study, to the accredited METC and the Competent Authority.

11.5 Public disclosure and publication policy

The CCMO statement regarding publication policy of the study results is subscribed.

